## 15. STATISTICAL CONSIDERATIONS

### 15.1. Organisation of the TEAM trial

The *TEAM* trial is a single trial consisting of 7 separately managed country-specific trials within 8 participating countries. Each country has its own protocol, CRFs and database. The trials are very similar to each other in design, with efforts made to ensure that data are compatible. The countries have their own sub-studies asking questions which will be answered with their own patients. Each country's trial data will be collated by the Central Data Centre and primary and secondary efficacy analyses and safety analyses will be carried out centrally. Each country-specific trial has a Chief Investigator and a Country Trial Steering Committee.

The overall trial is managed by an International Steering Committee consisting of all of the Chief Investigators, a statistician from the Central Data Centre and representatives from Pfizer Inc. There is an Independent Data Monitoring Committee consisting of a biostatistician and 4 oncologists, 2 each from Europe and North America who meet regularly to evaluate the progress of the trial and make recommendations on whether to continue. There is also a sub-committee of the Steering Committee called the Data Management Committee, which consists of 4 of the Chief Investigators, the biostatistician from the Central Data Centre and representatives of Pfizer Inc.

The Central Data Centre is located at the Leiden University Medical Centre in the Netherlands. Data from all countries involved is collected in/transferred to the central database on a regular basis prior to DMC and Steering Committee meetings.

### 15.2. Hypothesis and sample size

In the amended protocol (27th October 2004), patients in the tamoxifen arm are assumed to switch to exemestane after 2¾ years (range from 2½ -3 years) of treatment with tamoxifen. The main goals of this study are to compare the DFS among patients who received either exemestane 25 mg or tamoxifen for 2.5- 3 years followed by 2.5- 2 years of exemestane for 2.75 years (i.e. 33 months), and for 5 years. Overall survival and DFS at 10 years will be evaluated. The safety for both arms at 2.75 years and 5 years will also be assessed.

The ATAC paper provided updated information comparing tamoxifen and anastrozole. The 3-year DFS rate was estimated to be approximately 90% for the tamoxifen arm (i.e., Arm B before switch). If the hazard ratio of DFS is assumed to be 1.28 between the two treatment arms (Arm B / Arm A), **723 events** will achieve 87% power to detect the corresponding difference in DFS with a two-sided significance level of 0.0298. Assuming constant exponential rates in both groups with a hazard ratio of 1.28), **9300 patients (4650 in each group) are sufficient in order to observe these 723 events after each subject is followed for 2.75 years.** The Independent Data Monitoring Committee, as part of their evaluation of the progress of the trial, will review an interim analysis at the time 50% of the events are reported for the first co-primary endpoint, at or before 2.75 years from the time of randomization.

The entire TEAM trial will accrue a total of 9300 patients in order to observe 723 DFS events at 2.75 years (33 months). UK will contribute approximately 1200 patients.

**Timing of the first primary analysis of DFS:** approximately 2¾ years after the last patient has been enrolled when there will be at least 723 events. Based on this, the following hypotheses are stated:

**A:** under the null-hypothesis ( $H_0$ ) if there is no difference between the two treatments, assuming the 3-year DFS is 90%, then: treatment arm A (tamoxifen) and treatment arm B (exemestane) will show a 3 years DFS of 90%.

**B:** under the alternative hypothesis ( $H_1$ ) the HR is 1.28 for the first 2¾ years and hence ( $H_0$ ) is rejected.

### 15.3. Rationale for type of analysis and trial organisation

This country-specific study is designed to be a part of a larger group of studies that will be pooled in order to test DFS and OS. A total of 723 events are needed in order to test for a reduction in the DFS between the two treatment arms when the true hazard ratio is 1.28.

The rationale for testing using multiple studies and testing using a pooled analysis as opposed to conducting one large multi-national study is that many additional questions of interest that do not require such a large sample size can be answered. The reporting of one study's main objective will not be delayed while waiting for the other studies to finish and therefore, not delaying the release of important clinical results. In addition, the CRFs will be more manageable and data clean up will be simplified.

The data from all the trials will be collected periodically throughout the trial and stored in a central database located at the Leiden University Medical Center in the Netherlands. Interim and final analyses for the combined trial will be conducted in this central location.

There are six major areas in which a meta-analysis might lead to misinterpretation: study design, combinability, heterogeneity of studies, statistical analysis, sensitivity analysis and control of bias. The confidence one places in the results of any such meta-analysis is limited by the combinability of the studies; that is inherent differences in design, sample, and endpoints. Thus, the greater the similarities of the studies with regard to those points, the greater the confidence one may have in the results of a meta-analysis.

The *TEAM* trial, of which this trial is a part, is different from trials usually analysed with meta-analytic methods. The data in this trial can be pooled because the studies will all be similar in patient population, design, duration, endpoints, and will use similar forms for data collection. Care will be taken to test for heterogeneity of studies and to incorporate any such heterogeneity into the statistical analysis. As this is a pre-specified pooling it will not be subject to the usual issues facing a meta-analysis such as publication bias (the phenomenon in which studies with positive results are more likely to be published than studies with negative results), which is often the largest bias of meta-analysis results.

### 15.4. Efficacy analysis

#### 15.4.1 First co-primary efficacy analysis

The first co-primary efficacy endpoint will be the DFS at 2.75 years post-treatment (before tamoxifen arm switching to exemestane), as estimated from the Kaplan-Meier curves for each

treatment arm. The difference in DFS will be assessed using the log-rank test at the 5% significance level, with a 90% power to detect absolute differences of 2%-3%.

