### **15.6. Interim Analysis**

The entire TEAM trial will accrue a total of 9300 patients in order to observe 723 DFS events in the first co-primary endpoint at 2.75 years. Safety analyses will be reported to the Independent Data Monitoring Committee (IDMC) every 6 months without evaluation of efficacy. The number of efficacy events will be monitored centrally every 3 months and reported to the IDMB. One interim efficacy analysis is planned for the first co-primary endpoint, to be reviewed by the IDMC. As part of their evaluation of the progress of the trial, they will review an interim analysis of the combined TEAM trial at the time 50% of the events are reported for the first co-primary endpoint, at or before 2.75 years from the time of randomization when half of the required number of DFS events for the first co-primary endpoint have occurred. These unblinded data will only be reviewed by IDMC members. The primary objective of the interim analysis is the early detection of either alarming side effects, intolerability to the treatment regimens, or of large differences in treatment effects.

The overall alpha-level for the first co-primary analysis will be maintained at 0.0302 using an O'Brien-Fleming-type alpha-spending function. The levels of significance at the interim analysis and at the final analysis for the first co-primary endpoint are 0.0012 and 0.0298, respectively.

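### Section 15.4.1 tests the first co-primary endpoint at 5%, but Sections 15.2 and 15.6 set the same final test at two-sided 0.0298 (0.0302 overall), and the protocol does not say which governs

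*Protocol*

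**What the plan says.** Three sections of the protocol fix the significance level of one test, the comparison of DFS at 2.75 years.

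- **Section 15.4.1 (first co-primary efficacy analysis):** "The difference in DFS will be assessed using the log-rank test at the 5% significance level, with a 90% power to detect absolute differences" of 2 to 3 percentage points. It does not state whether the test is one- or two-sided.
- **Section 15.2 (hypothesis and sample size):** 723 events "will achieve 87% power to detect the corresponding difference in DFS with a two-sided significance level of 0.0298", for a hazard ratio of 1.28.
- **Section 15.6 (interim analysis):** the overall level for this endpoint is 0.0302 under an O'Brien-Fleming-type spending function, with one look at half the events. "The levels of significance at the interim analysis and at the final analysis for the first co-primary endpoint are 0.0012 and 0.0298, respectively".

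The 87% power figure appears only in 15.2. Section 15.6 gives levels but no power. Nowhere is the 5% described as a family-wise level from which 0.0302 has been taken.

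**The concern.** The section an analyst would open to run the test gives a looser threshold than the two sections that size the trial and control its error. The conflict concerns the success criterion of a primary endpoint in an open-label trial. If the final p-value were 0.04, the trial would succeed under 15.4.1 and fail under 15.2 and 15.6. Either conclusion could be defended from the protocol, and the choice would be made after the p-value was known. Following 15.4.1 literally would also break the limit that 15.6 says is maintained.

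**Working it through.** **Inputs.** 723 events, hazard ratio (HR) 1.28, two-sided 0.0298, 87% power and 3-year DFS of 90% on tamoxifen (15.2); 1:1 allocation (6.1); interim at 50% of events, levels 0.0012 and 0.0298, overall 0.0302 (15.6); 5% and 90% power (15.4.1). I take the 5% as two-sided, as in 15.2.

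**1. Reproduce the 87% in 15.2.** With equal allocation, the expected log-rank z is √D/2 × ln(HR) = √723/2 × ln 1.28 = 13.444 × 0.2469 = 3.319.
- At 0.0298 the critical value is 2.173. Power = Φ(3.319 − 2.173) = 87.4% (Freedman's formula gives 87.1%). This matches 15.2.
- At 0.05 the critical value is 1.960. Power = Φ(3.319 − 1.960) = 91.3% (Freedman 91.0%).
- For 90% power at 0.0298, D = 4 × (2.173 + 1.282)² / (ln 1.28)² = 784 events (Freedman 792), against 723 planned.

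**2. Reproduce the levels in 15.6.** The interim and final statistics are bivariate normal with correlation √0.5.
- Overall error = 1 − P(|Z₁| < 3.239, |Z₂| < 2.173) = 0.0302, as stated.
- The O'Brien-Fleming-type spend at half information for 0.0302 is 4 × [1 − Φ(z(1 − 0.0302/4)/√0.5)] = 0.00118, that is 0.0012, as stated. The same formula for an overall 0.05 gives 0.0031, so the stated interim level belongs with 0.0302 and not with 5%.

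**3. Put 15.4.1's level into the same design.**
- Overall error = 1 − P(|Z₁| < 3.239, |Z₂| < 1.960) = 0.0503.
- 0.0503 / 0.0302 = 1.67.
- Nearly all of the excess comes from 0.05 against 0.0302. The interim look adds only 0.0003 to a 5% test.

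**4. Size of the ambiguous zone.** The observed hazard ratio at the boundary is exp(2z/√723).

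| Final level | Critical z | Observed HR at boundary |
|---|---|---|
| 0.0298 | 2.173 | 1.175 |
| 0.05 | 1.960 | 1.157 |

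Ignoring the interim look, the probability of a p-value between the two levels is 0.05 − 0.0298 = 2.0% under the null hypothesis, and 91.3% − 87.4% = 3.9% under HR 1.28.

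**5. The power wording.** With exponential rates, the tamoxifen hazard is −ln(0.90)/3 = 0.03512 per year.
- DFS at 2.75 years is exp(−0.0966) = 90.79% on tamoxifen and exp(−0.0966/1.28) = 92.73% on exemestane, a difference of 1.94 points.
- A difference of 2.0 points at 2.75 years corresponds to HR = ln(0.9079)/ln(0.9279) = 1.29, with 89.7% power at 0.0298.

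**The case against.** A careful reader would probably settle on 0.0298. Section 15.6 names it specifically as the final level for this endpoint, 15.2 agrees, and 15.4.1 stands alone. The zone in which the choice matters is narrow. This bears on how likely the conflict is to matter, but it does not remove it: 15.4.1 is current text and attaches the 5% to this particular log-rank test. An SAP that picked one level would still contradict a protocol section.

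Three stronger readings are tempting, and the document does not support them.

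- **The 90% in 15.4.1 is a second, separate contradiction.** The two power figures refer to slightly different alternatives. At 0.0298 the lower end of the 2 to 3 point range already has 89.7% power, and larger differences have more. Section 15.2 also analyses after every patient has 2.75 years of follow-up, with at least 723 events. Its own rates, with no dropout, give 4650 × (0.0921 + 0.0727), about 766 events, and about 89.3% power for HR 1.28. The power gap mostly follows from the gap in level.
- **The rest of a 5% error is reserved for the second co-primary endpoint, and 15.4.1 would use it up.** This is a plausible explanation of why 0.0302 is below 0.05, but the protocol never says so. Section 15.4.2 plans a point estimate, standard error and 95% confidence interval, with no test or level.
- **The interim look is what inflates the error.** It adds only 0.0003.

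**Conclusion.** The inconsistency is real and concerns the significance level. The protocol sets the first co-primary final test at 5% in one section and at two-sided 0.0298 in two others, without stating precedence. Sections 15.2 and 15.6 form one coherent design: 723 events, HR 1.28, 87% power, 0.0012 then 0.0298, 0.0302 overall. The 5% level does not fit it and would spend about 0.0503, roughly 1.7 times the stated cap. The outcome is ambiguous for final p-values between 0.0298 and 0.05. It should be corrected because it is the decision threshold for a primary endpoint. The power wording is secondary.

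These figures assume proportional hazards, equal allocation, a two-sided reading of the 5%, and an interim at exactly half the events. That 0.0298 governs is inferred from the agreement of 15.2 and 15.6, so the sponsor must confirm it.

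**What to change.** In 15.4.1, replace the 5% level with a two-sided level of 0.0298 at the final analysis (0.0012 at the interim, 0.0302 overall) and refer to 15.6, once the sponsor has confirmed that this level governs. As a consequential edit, replace the power clause with 87% power for a hazard ratio of 1.28, an absolute difference of about 1.9 percentage points at 2.75 years on the assumptions of 15.2.

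The cost is a change of wording and a slightly less favourable power statement. The number of events, the number of patients and the conduct of the trial stay as they are. If the sponsor instead holds that 5% governs, the levels and power in 15.2 and 15.6 would have to be derived again, because the 0.0302 cap could not stand.

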#### **15.4.2 Second co-primary efficacy analysis**

The second co-primary efficacy endpoint will be DFS at 5 years post-treatment as a point estimate obtained from the Kaplan-Meier survival estimates of the two treatment arms. The difference in 5-years DFS between the treatment arms will be reported, along with its standard error (SE) and an associated 95% confidence interval. . In addition, patients will be followed up for a minimum of 10 years and long term outcomes will be reported.

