##### Endpoints

###### Primary Endpoint

There are 2 co-primary objectives in this study:

[figure not shown]
- To determine whether adjuvant treatment with exemestane 25 mg once daily improves the disease free survival (DFS) of postmenopausal, receptor positive, node negative or node positive breast cancer patients at 2.75 years compared with adjuvant tamoxifen 20 mg once daily for 2.5 – 3 years, followed by exemestane, 25 mg once daily for 2 – 2.5 years. DFS is defined as the time from randomisation to the earliest recorded documentation of local/regional or distant recurrence of breast cancer, new 2nd primary (contra lateral) invasive breast cancer or death from any cause
- To determine whether adjuvant treatment with exemestane 25 mg once daily improves the disease free survival (DFS) of postmenopausal, receptor positive, node negative or node positive breast cancer patients at 5 years compared with adjuvant tamoxifen 20 mg once daily for 2.5 – 3 years, followed by exemestane, 25 mg once daily for 2 – 2.5 years

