##### **14.1. Disease-Free Survival (DFS)**

Disease-Free Survival (DFS) is defined as the time from randomization to the earliest recorded documentation of local/regional or distant recurrence of breast cancer, new 2nd primary (contralateral) invasive breast cancer or death from any cause. Patients who have not had any such event (relapse or death) at the time of data analysis will be censored at 2.75 years for the first co-primary endpoint and at the last date they were known to be event-free for the 2nd co-primary endpoint and the secondary endpoints. Kaplan-Meier estimates of the survival curves for each treatment arm (including medians and 95% confidence intervals) as well as the result of the log-rank test will be presented.

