#### **15.4.3 Secondary efficacy analysis**

The secondary efficacy endpoints will be 5 and 10 years overall survival and 10 years disease free survival, comparing exemestane vs. tamoxifen followed by exemestane as estimated from the Kaplan-Meier curves for each treatment arm. The difference in 5 and 10 overall survival and 10 years disease free survival between the treatment arms will be reported, along with its standard error (SE) and an associated 95% confidence interval. In addition, patients will be followed up for a minimum of 10 years and long term outcomes will be reported.

For the primary efficacy analyses, Cox regression models will be used to explore the influence of stratification and prognostic factors on DFS. Each factor will be evaluated for inclusion in the multivariate model, and only factors significant at the 10% level will be considered. The secondary efficacy analysis, i.e. the results of the patients who received both medications sequentially due to the “cross-over” design, will be analysed on an exploratory basis since the proportional hazards model may not be appropriate for these patients.

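### The second co-primary endpoint has a Kaplan-Meier difference fixed at 5 years and a log-rank test with no 5-year limit, and the protocol does not say which one decides

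*Protocol*

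**What the plan says.** The second co-primary objective (protocol section 5, Primary Endpoint) concerns DFS in "breast cancer patients at 5 years compared with adjuvant tamoxifen 20 mg once daily for 2.5 – 3 years", followed by exemestane.

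Section 15.4.2 makes the endpoint "DFS at 5 years post-treatment as a point estimate obtained from the Kaplan-Meier survival estimates". On reporting it says: "The difference in 5-years DFS between the treatment arms will be reported, along with its standard error (SE) and an associated 95% confidence interval". It names no test, significance level or decision rule.

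Section 14.1 defines DFS for all endpoints together. Event-free patients "will be censored at 2.75 years for the first co-primary endpoint", but "at the last date they were known to be event-free for the 2nd co-primary endpoint and the secondary endpoints". It then says that Kaplan-Meier curves "as well as the result of the log-rank test will be presented".

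Section 15.4.1 names the log-rank as the test for the first co-primary. Section 15.6 assigns that endpoint an overall alpha of 0.0302. No section assigns an alpha to the second co-primary.

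**The concern.** For the first co-primary the pieces fit: the data stop at 2.75 years and the named test uses those data. For the second they do not. The Kaplan-Meier difference answers a question about 5 years. The log-rank in 14.1 runs to each patient's last event-free date, so it answers a question about all follow-up. Recruitment began in December 2001 (section 3, Preface) and was still open at the amendment of 27 October 2004 (sections 4 and 15.2). Accrual is therefore close to 3 years or more, and early patients will have well over 5 years of data once the last patient reaches 5.

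A co-primary endpoint needs one deciding analysis, fixed before the data are seen. As written, someone holding both results could present either as the co-primary result. At stake is the error rate for this endpoint and, in some scenarios, the conclusion itself.

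**Working it through.** **1. The plan's own figure.** The only power statement is for the first co-primary: 723 events "will achieve 87% power to detect the corresponding difference in DFS with a two-sided significance level of 0.0298". By Schoenfeld's formula, power = Φ(√(723/4) × ln 1.28 − z(1 − 0.0298/2)) = 87.4%, which agrees. The interim and final levels of 0.0012 and 0.0298, at half the information, combine to 0.0302 by the bivariate normal, as stated. If the total is 0.05, then 0.05 − 0.0302 = 0.0198 remains, but the protocol does not assign it. No power is given for the second co-primary.

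**2. The two co-primaries side by side.**

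| | First co-primary | Second co-primary |
|---|---|---|
| Question | DFS at 2.75 years | DFS at 5 years |
| Censoring (14.1) | 2.75 years | last event-free date |
| Analysis (15.4) | log-rank, named as the test | Kaplan-Meier difference, SE, 95% CI; no test |
| Log-rank horizon | 2.75 years | all follow-up |

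**3. How often the two verdicts differ.**

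Inputs from the protocol: 9300 patients, 4650 per arm; 3-year DFS of 90% on tamoxifen, so a hazard of −ln(0.9)/3 = 0.0351 per year; hazard ratio 1.28, stated for the first 2¾ years only, so an exemestane hazard of 0.0351/1.28 = 0.0274.

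Assumptions not in the protocol: uniform accrual over 4 years, cut-off 5 years after the last patient, no loss to follow-up, two-sided alpha 0.05, and the hazard ratio after 2.75 years.

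Statistics: z = [S_E(5) − S_T(5)] / √(V_E + V_T) with Greenwood variances for the Kaplan-Meier difference; z = (O − E)/√V for the log-rank, once on all follow-up and once truncated at 5 years. There were 3000 simulated trials per row, so the Monte Carlo standard error is at most about 0.9 percentage points.

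| True hazard ratio | All-follow-up log-rank significant | KM difference at 5 years significant | Verdicts differ | Verdicts differ if log-rank stops at 5 years |
|---|---|---|---|---|
| 1.0 (null) | 5.1% | 5.2% | 5.2% | 0.3% |
| 1.28 throughout | 100% | 99.4% | 0.5% | 0.1% |
| 1.28, then 1.0 (both at tamoxifen hazard) | 59% | 67% | 17% | 3.6% |
| 1.28, then 1.0 (both at exemestane hazard) | 63% | 73% | 18% | 2.9% |
| 1.10 throughout | 56% | 44% | 20% | 1.4% |
| 1.15 throughout | 86% | 74% | 15% | 1.3% |

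Over repeat runs the disagreement was 16-19% for 1.28 then 1.0, 14-20% for constant 1.10-1.15, 0.1-1% for constant 1.28 and 4-5% under the null.

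**4. Error if either result counts.** P(either) = [P(A) + P(B) + P(differ)]/2 = (5.1 + 5.2 + 5.2)/2 ≈ 7.7%, against 5%. Repeat runs gave about 7-8%.

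**5. Sensitivity to the assumed calendar (1.28 then 1.0).** With the cut-off 5 years after the last patient, accrual of 1, 3 and 5 years gives disagreement of 9.5%, 16% and 22%. A cut-off 2.75 years after the last patient (5 years' accrual) gives 14%. A cut-off 10 years after (4 years' accrual) gives 36%.

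**The case against.** The best defence is that 15.4.2 is the section written for this endpoint, so it governs. Section 14.1 says only that the log-rank will be presented, whereas 15.4.1 says that the first co-primary will be assessed by it. On that reading the log-rank merely accompanies the curves. It is a fair reading, and it means the protocol does not declare two rival tests. It does not settle the matter. Section 14.1 uses one sentence for both co-primaries, and for the first the log-rank it mentions is the deciding test. Nothing marks it as supportive for the second, and 15.4.2 offers no test in its place. A SAP that is not shown may assign the roles, but the protocol's own horizon mismatch would remain.

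It is also true that the censoring rule does no harm to the Kaplan-Meier estimate at 5 years, which uses only data up to 5 years. The problem lies in the log-rank attached to that rule.

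Three stronger readings are tempting and are not supported:

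- **That the two analyses disagree in one trial in five as a rule.** That rate needs an effect that ends at the switch, or a modest constant one, together with an assumed calendar. If 1.28 persists, disagreement is about 1% or less.
- **That the all-follow-up log-rank is the weaker analysis.** It is weaker if the effect stops at 2.75 years and stronger at a constant 1.10 or 1.15. The protocol assumes nothing about the effect after 2.75 years.
- **That the protocol itself doubts proportional hazards for this endpoint.** The caveat, "since the proportional hazards model may not be appropriate for these patients", is written in 15.4.3 for the exploratory secondary analysis of patients who took both drugs in sequence. It is relevant background, since the tamoxifen arm of the 5-year comparison is designed to take both, but it is not stated for the second co-primary.

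Finally, no section permits counting either result as success. The 7-8% is what the silence leaves open, not something that the protocol plans.

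**Conclusion.** The point stands in a limited form. For the second co-primary the stated log-rank does not share the 5-year horizon of the stated endpoint, and no analysis is named as deciding. That follows from the text and needs no simulation.

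The practical size is conditional. It ranges from negligible, if the planned hazard ratio persists, to about one trial in six for an effect that stops at the switch. For a modest constant effect it is about one in seven to one in five. These figures rest on 4 years' accrual, a cut-off 5 years after the last patient, no loss and alpha 0.05; a different calendar moves the early-effect figure between about 10% and 36%. The documents do not support a general claim about which analysis has more power. This should be corrected, but it does not invalidate the design.

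**What to change.** - **15.4.2:** name one deciding analysis and state its share of alpha. Either the Kaplan-Meier difference at 5 years already described or a log-rank truncated at 5 years will do. With 5 years of follow-up on every patient, their statistics correlate at 0.999 and their verdicts agree in about 96% or more of trials in the scenarios tabulated. If the Kaplan-Meier difference decides, match the confidence level of its interval to the alpha assigned.
- **14.1:** for this endpoint, censor the log-rank at the earlier of the last event-free date and 5 years from randomisation. Label any log-rank over all follow-up as supportive.
- **15.4.2:** change 'post-treatment' to 'from randomisation', to match the DFS definition in 14.1.
- **Timing:** run the analysis when every patient has had the opportunity for 5 years of follow-up. With a cut-off only 2.75 years after the last patient (5 years' accrual, 1.28 then 1.0), even the truncated log-rank and the Kaplan-Meier difference disagree in about 14% of trials.

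The cost is a few sentences of analysis wording, with no new patients, visits or data items.
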